**Primary Objectives:**

- Assessment of retrograde urine reflux after placement of a ureteral stent using cystography after contrast gravity-filling of the bladder and assigning a urinary reflux grade based on the following standardized scoring system:
  - Grade I: urine refluxes into the ureter only.
  - Grade II: urine refluxes into the ureter and up to the kidney without dilation.
  - Grade III: urine refluxes into the ureter and kidney and causes mild dilation.
  - Grade IV: urine refluxes into ureter and kidney and causes dilation without twisting of the ureter.
  - Grade V: urine refluxes into ureter and kidney and causes significant dilation with twisting of the ureter.

- Evaluation of the stent placement and the adequacy of short-term drainage (defined as the presence of the stent in the ureter and the lack of surgical or other intervention to treat symptoms associated with the stent itself on the stented side during the first 48 hours).

[figure not shown]

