**Study Endpoints:****1- Primary effectiveness endpoint:**

- Study success defined as adequate short-term drainage defined as the presence of the stent in the ureter and the lack of surgical or other intervention to treat symptoms associated with the stent itself on the stented side during the first 48 hours [Day 0-2] following placement.
- [Note: In some cases, the ureteral stent may not be sufficient to relieve pain (not associated with stent specifically) and alternative surgical treatment may be warranted. In these cases, patient data will be captured but non-device related cause captured as reason for subject stenting termination.]
- Assessment of retrograde urine reflux after placement of the ureteral stent, as determined by the visualization of urine in the distal ureter to the kidney using cystography after contrast gravity-filling of the bladder and assigning a urinary reflux grade based on:
  - Grade I: urine refluxes into the ureter only.
  - Grade II: urine refluxes into the ureter and up to the kidney without dilation.

- Grade III: urine refluxes into the ureter and kidney and causes mild dilation.
- Grade IV: urine refluxes into ureter and kidney and causes dilation without twisting of the ureter.
- Grade V: urine refluxes into ureter and kidney and causes significant dilation with twisting of the ureter.

- Visualization of distal coil in bladder, after stent placement. Document placement using a cystoscope.

2- Primary safety endpoint:  
Assessment of pain or irritative symptoms (incidence, severity) attributed to the ureteral stent as well as unplanned return visits to ED, OR, or clinic.

3- Secondary endpoint:

- USSQ Scale (Ureteral Stent Symptoms Questionnaire) [Time Frame: Day 3 as endpoint]
- Unplanned hospital visits or doctor visits related to the stent
- Medication use endpoint:
  - Physicians can prescribe standard medications such as alpha blocker (Tamsulosin), Anticholinergic (Oxybutynin), phenazopyridine (Pyridium), ibuprofen and Tylenol prn pain for the duration of the stent plus 1 day (post stent removal) (Document on CRF)
  - Requests for “breakthrough” pain medication (narcotics) would be at the request of the patient post procedure (not to be given as a standard dose). (Document on CRF)
  - Patients to keep medication diary in situations where patients are not taking medications as prescribed

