## 6 STUDY INTERVENTION

### 6.1 STUDY INTERVENTION(S) ADMINISTRATION

### 6.1.1 STUDY INTERVENTION DESCRIPTION

The study intervention is placement of the RELIEF Ureteral Stent, and the control product is the Ascerta stent by Boston Scientific. Placement of the stent is described in section 4 of the protocol.

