## 6.2 PREPARATION/HANDLING/STORAGE/ACCOUNTABILITY

### 6.2.1 ACQUISITION AND ACCOUNTABILITY

The Relief stent is provided from the company at no charge. The control stent is our current standard stent (Ascerta by Boston Scientific) which is available in stock. Both will be kept in an OR storage location, and the Relief stent will have a notice that it is for research purposes and not to be used outside of this study and without instruction by the study PI and coordinator.

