## 7.2 PARTICIPANT DISCONTINUATION/WITHDRAWAL FROM THE STUDY

Participants are free to withdraw from participation in the study at any time upon request.

An investigator may discontinue or withdraw a participant from the study for the following reasons:

- Pregnancy
- Significant study intervention non-compliance
- If any clinical adverse event (AE), laboratory abnormality, or other medical condition or situation occurs such that continued participation in the study would not be in the best interest of the participant
- If the participant meets an exclusion criterion (either newly developed or not previously recognized) that precludes further study participation

The reason for participant discontinuation or withdrawal from the study will be recorded on the Withdrawal Case Report Form (CRF). Research participants who sign the informed consent form and are randomized but do not receive the study intervention may be replaced. Research participants who sign the informed consent form, and are randomized and receive the study intervention, and subsequently withdraw, or are withdrawn or discontinued from the study, will not be replaced.

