# 8 STUDY ASSESSMENTS AND PROCEDURES

## 8.1 EFFICACY ASSESSMENTS

The primary objective of the study is to assess whether the Relief stent causes reflux of urine. This will be assessed using a standardized grading system described previously. The additional objective of evaluating adequacy of short-term drainage uses the following definition: presence of stent in the ureter and lack of surgical or other intervention to treat symptoms associated with the stent itself during the first 48 hours. This will be determined during the phone interview or in person visit with the patient on

days 1 and 3 as well as by questionnaire. Medications used will be tracked on the research form per the timeline at days 1, 3, 7-10.

Screening will occur in the clinics to identify patients with stone disease who meet eligibility requirements and who require surgical treatment for their stones.

Patients who are deemed clinically suitable and choose to participate will be screened utilizing the EMR for recruitment. The urology provider will first determine if they are interested in participating in the research study and upon agreement, a study team member or research coordinator will introduce the study details and initiate a consent interview. If eligible, these patients will be approached during pre-surgical preoperative clinic visits by the research team to further explain the study and further address any of their questions and get their consent. Patients will be free to leave the study without any impact or influence on their clinical care or management at any point should they desire to do so.

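### The replacement rule in Section 7.2, with no analysis set in Section 9.3, could let failed RELIEF placements go uncounted in placement and drainage success

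*Combined protocol and SAP*

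**What the plan says.** Section 7.2 sets the replacement rule: "Research participants who sign the informed consent form and are randomized but do not receive the study intervention may be replaced". Its next sentence rules out replacement once the intervention has been received. Section 6.1.1 fixes the term: "The study intervention is placement of the RELIEF Ureteral Stent, and the control product is the Ascerta stent by Boston Scientific".

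Under the primary objectives, Section 3 lists "Evaluation of the stent placement and the adequacy of short-term drainage". The primary effectiveness endpoint in the same section begins "Study success defined as adequate short-term drainage defined as the presence of the stent in the ureter" and adds that no intervention for stent symptoms is needed in the first 48 hours. The synopsis gives the same primary endpoint. Section 8.1 ranks it differently: reflux is the primary objective there, and drainage is introduced with "The additional objective of evaluating adequacy of short-term drainage uses the following definition".

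Section 7.1 keeps a patient in the study when a stent is not left in for its expected duration, and asks for the reason for early or late removal. It does not address a stent that was never placed. Section 9.3, on analysis populations, repeats the four inclusion criteria. Intention-to-treat appears only in the abbreviation list.

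The trial is open label with 25 patients per arm (Sections 4.1 and 9.2). Randomization is on Day 0. Section 5.2, item 8, allows an exclusion during surgery at the urologist's discretion, and the plan does not say whether this comes before or after randomization.

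**The concern.** Failure to place the assigned device is an outcome in a trial that evaluates stent placement. Under Section 7.2 the same event makes the patient replaceable. The decision is discretionary, can be made with the assignment known, and can come after the surgeon has seen the anatomy. With a target of 25 per arm, a replacement fills the slot, and nothing requires the replaced patient to be followed or analysed.

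If such patients are left out, RELIEF success is computed only among patients in whom RELIEF could be placed. If they were not followed, the loss cannot be repaired at the analysis stage.

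**Working it through.** **The plan's own figure.** Inputs from Section 9.2: N = 50, w = 0.4, alpha = 0.05. For a 1-df chi-square test the noncentrality is N × w² = 50 × 0.16 = 8 and the critical value is 3.841. Power is 80.7%, and the smallest N that reaches 80% is 50. The stated 80% reproduces, with almost no margin. It concerns reflux incidence, not placement or drainage.

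**Does the rule reach a failed placement?**
- Section 7.2: randomized and did not receive the study intervention, so may be replaced.
- Section 6.1.1: the study intervention is placement of RELIEF.
- Hence a patient randomized to RELIEF in whom it could not be placed falls within the rule.
- Neither Section 7.1 nor Section 9.3 brings that patient back into an analysis.

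**Effect on observed RELIEF placement success.** Let k be the number of failed placements. The documents give no value, so k is an assumption. For k above zero, the middle column assumes that each failure is replaced by one successful placement.

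| k | Not replaced: (25 − k)/25 | Replaced, all randomized analysed: 25/(25 + k) | Replaced, not analysed: 25/25 |
|---|---|---|---|
| 0 | 100% | 100% | 100% |
| 1 | 24/25 = 96% | 25/26 = 96.2% | 100% |
| 2 | 23/25 = 92% | 25/27 = 92.6% | 100% |
| 3 | 22/25 = 88% | 25/28 = 89.3% | 100% |

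The first two columns nearly agree. Replacement alone therefore does little harm; the distortion comes from leaving the replaced patients out. For k = 2 or 3 it is 100 − 92.6 = 7.4 points or 100 − 89.3 = 10.7 points. The exact 95% interval for 25/25 is 86.3% to 100%.

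**How likely is any failure?** The chance of at least one in 25 is 1 − (1 − f)^25. For assumed failure rates f of 2%, 5% and 10% it is 40%, 72% and 93%.

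**Cost to reflux power of keeping these patients by assigned arm.** Assume reflux of 70% with DJ and 30% with RELIEF. These rates are illustrative and give w = 0.4. Assume also that a fraction c of the RELIEF arm leaves with the other stent.
- c = 8% (2 of 25): RELIEF-arm reflux is 0.30 × 0.92 + 0.70 × 0.08 = 0.332, w = 0.368, noncentrality 50 × 0.368² = 6.8, power 74.0%.
- c = 12% (3 of 25): RELIEF-arm reflux is 0.30 × 0.88 + 0.70 × 0.12 = 0.348, w = 0.352, power 70.3%.

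**The case against.** Several stronger readings are tempting, and the documents do not support them.

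- *The rule removes failures from the trial.* It says that patients may be replaced, which adds a patient and does not delete one. Section 7.2 asks for withdrawal reasons on a CRF, and Section 8.3.4 records events from consent onward, so some trace may remain. This stands: the loss is permitted, not ordered, and becomes real through the empty Section 9.3.
- *Failed RELIEF patients leave with the DJ stent.* No section says what happens after a failed placement. Section 6.2.1 says of the control stent only that it is one "which is available in stock". The point does not need this scenario, because any failed RELIEF placement triggers the rule.
- *The rule is built to act on one arm.* Read literally, Section 6.1.1 would make every control patient replaceable, which cannot be meant. Section 7.1 and the schedule of activities treat the stent as either device. The likely intent is the assigned stent. The wording needs repair, but it is no evidence of a one-sided design.
- *The reflux and symptom comparisons are biased.* Selective loss could affect them, but the documents give neither a size nor a direction.

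Two further objections stand in part. The powered endpoint is reflux, and Section 9 plans no drainage analysis. The 48-hour window also runs from placement, so a stent never placed is not clearly a failure as written. Both lower the stakes for the main test. The second is itself a reason to state how a failed placement is scored.

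**Conclusion.** The concern holds in a limited form. Sections 7.2 and 6.1.1 together allow a patient with a failed RELIEF placement to be replaced, and Section 9.3 contains nothing that keeps that patient in the count. The effect falls mainly on placement and drainage success, which the synopsis and Section 3 call primary but which is unpowered.

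The size depends entirely on an assumed number of failures. With none there is no effect. With 2 or 3, observed success could read 100% where counting all randomized patients gives 92.6% or 89.3%. That requires the replaced patients to be left out of the analysis, which the plan neither requires nor prevents. The text should be corrected before any replacement is made; the point does not invalidate the reflux comparison.

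**What to change.** 1. In Section 7.2, limit replacement in either arm to patients who never reach the point of stent placement, for reasons unrelated to the assigned stent.
2. Follow all other randomized patients and analyse them by assigned arm. Count failure to place the assigned stent as failure of the placement/drainage endpoint. Include a decision not to attempt it because of the device or the anatomy; otherwise the same selection returns by that route.
3. State this all-randomized set in Section 9.3 in place of the repeated inclusion criteria.
4. Reword Sections 6.1.1 and 7.2 so that the study intervention means the assigned stent in either arm.
5. State that randomization follows assessment of the intraoperative exclusion (Section 5.2, item 8), or else that patients excluded by it after randomization are reported by arm.

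The cost is a few sentences and one CRF field for the stent actually placed. The statistical price is dilution of the reflux contrast by any patient who leaves with the other stent: about 74% power at 8% crossover under the illustrative rates. This should be disclosed, since the design has no spare power. An as-treated reflux analysis can be reported as a sensitivity analysis.

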## 7.3 LOST TO FOLLOW-UP

A participant will be considered lost to follow-up if he or she fails to return for 3 scheduled visits and is unable to be contacted by the study site staff.

The following actions must be taken if a participant fails to return to the clinic for a required study visit:

- The site will attempt to contact the participant and reschedule the missed visit as soon as possible and counsel the participant on the importance of maintaining the assigned visit schedule and ascertain if the participant wishes to and/or should continue in the study.
- Before a participant is deemed lost to follow-up, the investigator or designee will make every effort to regain contact with the participant (where possible, 3 telephone calls and, if necessary, a certified letter to the participant's last known mailing address or local equivalent methods). These contact attempts should be documented in the participant's medical record or study file.
- Should the participant continue to be unreachable, he or she will be considered to have withdrawn from the study with a primary reason of lost to follow-up.

# 8 STUDY ASSESSMENTS AND PROCEDURES

## 8.1 EFFICACY ASSESSMENTS

The primary objective of the study is to assess whether the Relief stent causes reflux of urine. This will be assessed using a standardized grading system described previously. The additional objective of evaluating adequacy of short-term drainage uses the following definition: presence of stent in the ureter and lack of surgical or other intervention to treat symptoms associated with the stent itself during the first 48 hours. This will be determined during the phone interview or in person visit with the patient on

days 1 and 3 as well as by questionnaire. Medications used will be tracked on the research form per the timeline at days 1, 3, 7-10.

Screening will occur in the clinics to identify patients with stone disease who meet eligibility requirements and who require surgical treatment for their stones.

Patients who are deemed clinically suitable and choose to participate will be screened utilizing the EMR for recruitment. The urology provider will first determine if they are interested in participating in the research study and upon agreement, a study team member or research coordinator will introduce the study details and initiate a consent interview. If eligible, these patients will be approached during pre-surgical preoperative clinic visits by the research team to further explain the study and further address any of their questions and get their consent. Patients will be free to leave the study without any impact or influence on their clinical care or management at any point should they desire to do so.

## 8.2 SAFETY AND OTHER ASSESSMENTS

Case report forms will be generated for each subject and completed by the investigator or study coordinator. The investigator or study coordinator will countersign each form. After the case report forms for a visit are completed, the research coordinator will enter a limited set of data into a data management system. Original case report forms will be securely maintained at the clinical sites. Completed copies of the case report forms will be sent to the research coordinator where they will be stored on a secure hard drive. Subjects will be asked to report any adverse events to the study coordinator or physician. All adverse events will be reported on a standardized form that will elicit the number and specify the type of tests used, therapy (or therapies) used, and clinical visits (office, ER and hospitalization) required until the event is resolved.

## 8.3 ADVERSE EVENTS AND SERIOUS ADVERSE EVENTS

### 8.3.1 DEFINITION OF ADVERSE EVENTS (AE)

The FDA definition of an Adverse event is any untoward medical occurrence associated with the use of an intervention in humans, whether or not considered intervention-related (21 CFR 312.32 (a)).

### 8.3.2 DEFINITION OF SERIOUS ADVERSE EVENTS (SAE)

An adverse event (AE) or suspected adverse reaction is considered "serious" if, in the view of either the investigator or sponsor, it results in any of the following outcomes: death, a life-threatening adverse event, inpatient hospitalization or prolongation of existing hospitalization, a persistent or significant incapacity or substantial disruption of the ability to conduct normal life functions, or a congenital anomaly/birth defect. Important medical events that may not result in death, be life-threatening, or require hospitalization may be considered serious when, based upon appropriate medical judgment, they may jeopardize the participant and may require medical or surgical intervention to prevent one of the outcomes listed in this definition. Examples of such medical events include allergic bronchospasm requiring intensive treatment in an emergency room or at home, blood dyscrasias or convulsions that do not result in inpatient hospitalization, or the development of drug dependency or drug abuse.

### 8.3.3 CLASSIFICATION OF AN ADVERSE EVENT

### 8.3.3.1 SEVERITY OF EVENT

For adverse events (AEs) not included in the protocol defined grading system, the following guidelines will be used to describe severity.

- **Mild** – Events require minimal or no treatment and do not interfere with the participant's daily activities.
- **Moderate** – Events result in a low level of inconvenience or concern with the therapeutic measures. Moderate events may cause some interference with functioning.
- **Severe** – Events interrupt a participant's usual daily activity and may require systemic drug therapy or other treatment. Severe events are usually potentially life-threatening or incapacitating. Of note, the term "severe" does not necessarily equate to "serious".

### 8.3.3.2 RELATIONSHIP TO STUDY INTERVENTION

All adverse events (AEs) must have their relationship to study intervention assessed by the clinician who examines and evaluates the participant based on temporal relationship and his/her clinical judgment. The degree of certainty about causality will be graded using the categories below. In a clinical trial, the study product must always be suspect.

- **Definitely Related** – There is clear evidence to suggest a causal relationship, and other possible contributing factors can be ruled out. The clinical event, including an abnormal laboratory test result, occurs in a plausible time relationship to study intervention administration and cannot be explained by concurrent disease or other drugs or chemicals. The response to withdrawal of the study intervention (DE challenge) should be clinically plausible. The event must be pharmacologically or phenomenologically definitive, with use of a satisfactory rechallenge procedure if necessary.
- **Probably Related** – There is evidence to suggest a causal relationship, and the influence of other factors is unlikely. The clinical event, including an abnormal laboratory test result, occurs within a reasonable time after administration of the study intervention, is unlikely to be attributed to concurrent disease or other drugs or chemicals, and follows a clinically reasonable response on withdrawal (dechallenge). Rechallenge information is not required to fulfill this definition.
- **Potentially Related** – There is some evidence to suggest a causal relationship (e.g., the event occurred within a reasonable time after administration of the trial medication). However, other factors may have contributed to the event (e.g., the participant's clinical condition, other concomitant events). Although an AE may rate only as "possibly related" soon after discovery, it can be flagged as requiring more information and later be upgraded to "probably related" or "definitely related", as appropriate.
- **Unlikely to be related** – A clinical event, including an abnormal laboratory test result, whose temporal relationship to study intervention administration makes a causal relationship improbable (e.g., the event did not occur within a reasonable time after administration of the study intervention) and in which other drugs or chemicals or underlying disease provides plausible explanations (e.g., the participant's clinical condition, other concomitant treatments).
- **Not Related** – The AE is completely independent of study intervention administration, and/or evidence exists that the event is definitely related to another etiology. There must be an alternative, definitive etiology documented by the clinician.

### 8.3.3.3 EXPECTEDNESS

The study PI and Sponsor will be responsible for determining whether an adverse event (AE) is expected or unexpected. An AE will be considered unexpected if the nature, severity, or frequency of the event is not consistent with the risk information previously described for the study intervention.

